6.7.3 Rectal Swab

The collected rectal swab (see APPENDIX VI for details) will provide researchers with a tool to analyze the gut microbiome of patients in an effort to investigate potential correlations between the gut microbiome and response to cancer therapies. Consented patients will be asked to self-collect two rectal swabs during an office visit by inserting a cotton tipped application approximately 3 cm (about 1 inch) into the anal canal and rotating it. The swab can then be returned to the provided tube. Rectal swabs (two per specified time-point) will be collected at enrollment within 1-mos of randomization but prior to SABR or radium-223 infusion and at the 3-month time points.

Only participating sites that have the resources to do so, will participate in rectal swab collection.

6.7.4 Rectal Swab Processing

The collected swabs will be immediately stored at 4° C to prevent bacteria growth before being moved to -20/-80° C. Collected swabs will be processed for DNA extraction and eventual next generation sequencing to provide a genomic profile of the bacteria present in the gut microbiome of patients.

6.7.5 Invitae Genomic Testing

Consented patients will be asked to provide a blood or saliva sample during an office visit or at home, via an Invitae collection kit (see APPENDIX VII for details). **This collection will be performed on all enrolled patients, at any time point during study or after completion of study (F/U), regardless of their randomization arm.** The Invitae collection kit will then be activated online and dropped in the mail. Invitae will then analyze the genes from the patient’s blood or saliva sample. Once the patient’s results are ready, an email will be sent by Invitae prompting the PI to log into his established Invitae account and view the results. The patient will be allowed to make an appointment with one of the Invitae’s genetic counselors at no cost. Further, Invitae will also keep the patient updated if any information related to their results changes.

6.8 Duration of Therapy

Within three weeks of the initial treatment planning imaging study, SABR will be administered in a 1-5 fractions to each treated site (within 60 days from randomization) of the study and coincides with delivery of fraction 1.

Within four weeks of randomization to the SABR + Radium-223 arm, men will receive their 1st of 6 monthly infusions of radium-223.

6.9 Duration of Study Accrual

A trial with a similar patient population took 2 years to screen 60-70 patients. Thus we anticipate this study will last 3 years.

6.10 Duration of Follow-Up

Patients will be followed for 2-years, after Day one. Importantly, this follow-up period will include the collection of all Skeletal Related events.

6.11 Criteria for Patient Removal

Diagnosis of >3 bone and/or soft tissue metastases on entry imaging studies before SBRT/SABR. PSA >50 ng/ml before SABR. Progression as defined in section 9.5.5.

Radium-223 administration may be delayed by no more than four weeks for recovery of adverse events. In case of a treatment delay greater than four weeks, treatment should be discontinued. It is important to note that in general (unless otherwise agreed), in cases where study drug has been ordered, the time window is reduced to -3 days to + 3 days, due to decay. If administration has to be postponed more than 3 days after drug has been ordered, replacement of the drug order is required. Dose reduction for radium-223 will not be permitted and subjects with any toxicity requiring radium-223 dose reduction must discontinue radium-223 treatment.

Any toxicity requiring radium-223 discontinuation will be recorded as an AE in the subject's medical record and on the CRF.

6.12 Alternatives

The study has been designed to minimize potential risks to participants. First, this population of asymptomatic oligometastatic men is heavily pre-selected based on institutional data, STOMP and on-going ORIOLE phase II randomized data indicating that similar men will progress in 6-12-months (72-74). Secondly, the level of clinical-radiographic interrogation will allow both arms to be safely transitioned to standard of care treatments that can be initiated within a typical interval between clinic visits (72-74). Lastly, the SABR dose has been shown to be safe in previous trials. Risks to confidentiality will be minimized by having access to study records available only to the investigators with the exception of the standard clinical records (lab values, dictations, operative notes, etc).

Standard therapies for metastatic prostate disease include radiotherapy, ADT or observation. Such treatment may or may not be applicable for patients enrolled in this study. Regardless, patients will be expected to forgo standard treatment until there is evidence of clinical, biochemical (PSA >50 ng/ml) or radiographic disease progression.

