5. PARTICIPANT SELECTION AND ENROLLMENT PROCEDURES

All patients will be eligible to receive systemic therapy alone at the time of clinical or radiographic disease progression.

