6.15 Withdrawal from Study

In accordance with the Declaration of Helsinki, patients have the right to withdraw from the study at any time for any reason, without prejudice to their medical care. The investigator also has the right to withdraw patients from the study for any of the following reasons:

- Subject withdraws consent for follow-up.
- Subject is lost to follow-up.
- Study is terminated for any reason.
- Occurrence of AEs, if discontinuation of study medication is considered necessary by the Investigator and/or patient.
- Lack of patient compliance.
- Protocol violation.
- Progressive disease as defined in section 9.5.5.

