9.5.5 Clinical Response Parameters

Progression is a composite endpoint defined from the Prostate Cancer Working Group 2 (PCWG2) criteria for metastatic castrate resistant prostate cancer (mCRPC) (75) and our previous trials in a population of men with biochemical failure without metastases (72-74). Progression will be defined as either: 1) a $\geq 25\%$ increase in PSA from nadir (and by ≥ 2 ng/mL), requiring confirmation ≥ 4 weeks later (PCWG2 criteria); and/or, 2) clinical/radiographic-progression defined as symptomatic progression (worsening disease-related symptoms or new cancer-related complications), or radiologic progression (on CT scan: $\geq 20\%$ enlargement in sum diameter of soft-tissue target lesions [RECIST 1.1 criteria]; on bone scan: ≥ 1 new bone lesions), initiation of ADT or death due to any cause, whichever occurs first. Death is considered a severe adverse event here.

Progression Free Survival (PFS) is defined as the time from starting treatment to the time of progression as defined above. Subjects who do not progress will be censored at the time of the last contact.

ADT Free Survival (ADT-FS) is defined as the time from starting treatment to the time of initiation of palliative ADT. ADT will typically be initiated on tumor progression and/or development of new metastases. Subjects who do not start ADT will be censored at the time of the last contact.

Time to Progression (TTP) is defined as the time from starting treatment to the time of first documented tumor progression or new lesions by CT and/or bone scan or initiation of ADT. Subjects who do not progress will be censored at the time of the last contact. In addition, death from any cause will also be censored.

Time to New Metastasis (TNM) is defined as the time from starting treatment to the time of a new documented tumor metastasis by CT and/or bone scan. Subjects who do not progress will be censored at the time of the last contact.

Overall Survival (OS) is defined as the time from starting treatment until death due to any cause. For subjects who do not die, time to death will be censored at the time of last contact.

Locoregional Control (LRC) is defined as the time from starting treatment until local and/or regional relapse is documented

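### ADT-free survival is given two different start dates, and withdrawal from the study at progression could censor it informatively

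*Combined protocol and SAP*

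**What the plan says.** **Time origin.** Section 9.5.5 has ADT-FS "defined as the time from starting treatment to the time of initiation of palliative ADT". Section 14.1.2 has it run from the day of randomization. PFS is split in the same way: start of treatment in 9.5.5, date of randomization in 14.4.

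**Gap between the two dates.** Section 6.2 places Day 1 within 30 days of randomization. Section 6.8 allows SABR up to 60 days after randomization and the first radium-223 infusion up to four weeks after it.

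**Leaving the study.** Section 6.11 lists "Progression as defined in section 9.5.5" among the removal criteria. Section 6.15 gives the investigator the right to withdraw a man from the study for "Progressive disease as defined in section 9.5.5". That definition is a composite. One component is a 25% or greater "increase in PSA from nadir (and by" 2 ng/mL or more), confirmed at least four weeks later, so a PSA rise alone qualifies.

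**Follow-up and censoring.** Section 9.5.5 censors men without ADT at last contact. Sections 6.7.1, 6.10 and 14.2 provide two years of follow-up. The only rule in 14.2 for follow-up after withdrawal concerns men withdrawn for adverse events.

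**Start of ADT.** Section 6.12, which lists ADT as a standard treatment, says that "patients will be expected to forgo standard treatment until there is evidence of clinical, biochemical" (PSA above 50 ng/ml) or radiographic progression. Section 9.5.5 adds that "ADT will typically be initiated on tumor progression and/or development of new metastases".

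**Analysis.** Section 14.5 reports ADT-FS by Kaplan-Meier curve and median, with no test.

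**The concern.** An endpoint needs one time zero. With two, an analyst must choose, possibly after seeing the data in an open-label trial. The choice may also act unequally on the arms, because the treatment windows differ. Counting from randomization protects the randomized comparison. Counting from treatment start does not, and it leaves no time zero for a man who is randomized but never treated.

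The second issue is what happens to ADT-FS when a man progresses without starting ADT. If he is withdrawn from the study and contact ends, he is censored when ADT has probably become more likely. Kaplan-Meier assumes that censored men have the same future risk as those still followed. That would fail here, and ADT-FS would look longer than it is.

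ADT-FS is a secondary endpoint, but section 4.5 treats deferral of ADT as a main clinical aim and cites ADT-FS medians from an earlier randomized trial. Readers will compare the arms even without a planned test.

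**Working it through.** **1. The plan's own figure.** No figure is given for ADT-FS. The design figure is for PFS in section 14.2: 30 per arm, 80% power, medians of 10 and 20 months, one-sided 0.1, 18 months of accrual plus 12 of follow-up.
- Event probability with λ = ln 2 / median: 1 − (e^(−12λ) − e^(−30λ)) / (18λ). This gives 0.751 and 0.509.
- Expected events: 30 × (0.751 + 0.509) = 37.8.
- Schoenfeld power: Φ(√(37.8 × 0.25) × ln 2 − 1.282) = 0.80.
- Dropout: 30 / 0.95 = 31.6, so 32 per arm and 64 in total.

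The stated design reproduces, and nothing below changes it.

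**2. Size of the origin gap.** For one man, ADT-FS from randomization equals ADT-FS from treatment start plus the days between the two dates. At 30.44 days per month, the ceilings are:

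| Window | Section | Largest gap |
|---|---|---|
| Day 1, both arms | 6.2 | 30 / 30.44 = 0.99 months |
| SABR | 6.8 | 60 / 30.44 = 1.97 months |
| First radium-223, combination arm | 6.8 | 28 / 30.44 = 0.92 months |

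The smallest gap is close to zero. If first radium-223 counts as starting treatment, the ceilings differ by arm: 1.97 months for SABR alone against 0.92 for the combination, a difference of 1.05 months. In that case counting from treatment start could take more time off the SABR arm. If the 30-day Day 1 window governs, the ceiling is 0.99 months in both arms. The documents give no actual treatment delays, so no average gap can be computed.

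**3. Censoring after progression, read in sequence.**
- A confirmed PSA rise of 25% and 2 ng/mL meets 9.5.5, so PFS has its event.
- Section 6.12 does not expect ADT at that point unless PSA exceeds 50 or there is clinical or radiographic progression. ADT-FS may therefore have no event yet.
- Section 6.15 permits withdrawal from the study at that same point.
- If contact then ends, 9.5.5 censors ADT-FS there.
- The men censored are those who have just progressed. If they are nearer to ADT than the men still at risk, the Kaplan-Meier estimate is too high.

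The size depends on how many men are withdrawn in this way and how soon they start ADT. The documents give neither. PFS does not share this problem, because these men already have a PFS event.

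**The case against.** **Follow-up is largely provided for.** Sections 6.10 and 14.2 follow men for two years with no exception for progression. Section 6.7.1 says that the study team collects two-year information at all sites. The calendar footnotes require changes in concomitant medication at months 18 and 24, which would show an ADT start. Section 6.15 gives a right, not a duty, and removal in 6.11 can be read as coming off protocol treatment. This stands in large part. A reader might infer that every man with PSA progression is lost to ADT-FS follow-up, and the documents do not support that. What remains is that 6.15 speaks of leaving the study, and no sentence says that ADT start is still collected afterwards.

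**The origin gap is small.** True. A reader might set 2.0 months against a median ADT-FS and call it a shift in that median. It is the most that one man's time can move. The two definitions still cannot both be used.

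**A reader might also infer that the sections conflict on when PSA-only progression should lead to ADT.** The text does not bear this out. Only 6.12 sets an expectation, and it applies to both arms. Section 5 is permissive: "All patients will be eligible to receive systemic therapy alone at the time of clinical or radiographic disease progression". Sections 9.5.5 and 14.1.2 describe what typically happens. None of these three names the 25% and 2 ng/mL rise as a reason for ADT. Estimating the wait until PSA passes 50 would require nadirs and post-treatment doubling times that the documents do not give. Making PSA above 50 a binding trigger would be a debatable clinical choice, and it is not proposed here.

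**Conclusion.** Wrong as written, and minor. The conflict over the ADT-FS time origin is explicit in the text and needs no assumption. Its ceiling per patient is about 1.0 month under the Day 1 window. Under section 6.8 it is 2.0 months for SABR, against 0.9 in the combination arm if first radium-223 counts as starting treatment. The same mismatch touches PFS, where 14.4 already gives randomization and the intent-to-treat population. This does not show that the planned primary analysis is invalid.

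The censoring point is conditional. It holds only if investigators use the right in 6.15 and contact then ends. The bias would be upward if men who have just progressed are nearer to ADT than those still followed. Its size is unknown.

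**What to change.** In section 9.5.5, define ADT-FS and PFS from the date of randomization, matching 14.1.2 and 14.4.

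In sections 6.11 and 6.15, state that removal or withdrawal for progression ends protocol treatment only, and that ADT start continues to be collected to 2 years unless the man withdraws consent.

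The cost is wording in three sections. The sample size, the visit schedule and the primary analysis in 14.4 do not change. The medication review at months 18 and 24 already provides a place to record ADT start.

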6.13 Costs

Every patient will be provided a copy of the Insurance and Research Participant Financial Responsibility Information Sheet. This document outlines the financial responsibilities for each study test and procedure based on a standard of care versus research analysis.

6.14 Compensation

Patients will not be financially compensated if they join the study.

6.15 Withdrawal from Study

In accordance with the Declaration of Helsinki, patients have the right to withdraw from the study at any time for any reason, without prejudice to their medical care. The investigator also has the right to withdraw patients from the study for any of the following reasons:

- Subject withdraws consent for follow-up.
- Subject is lost to follow-up.
- Study is terminated for any reason.
- Occurrence of AEs, if discontinuation of study medication is considered necessary by the Investigator and/or patient.
- Lack of patient compliance.
- Protocol violation.
- Progressive disease as defined in section 9.5.5.

7. INVESTIGATIONAL AGENT/DEVICE/PROCEDURE INFORMATION

7.1 Investigational Agent – Radium-223

This information is loaded into the IND application section of eIRB. Additional radiopharmaceutical information not listed below is downloaded on the FDA IND application in the supporting documents section of eIRB and available there for review.

7.2 Investigational Agent - ¹⁸F-DCFPyL (“PyL”)

This information is loaded into the IND application section of eIRB. Additional radiopharmaceutical information not listed below is downloaded on the FDA IND application in the supporting documents section of eIRB and available there for review.

8. STUDY CALENDARS

Study Calendars

In order to minimize the need for research-only in-person visits, telemedicine visits may be substituted for in person clinical trial visits or portions of clinical trial visits where determined to be appropriate and where determined by the investigator not to increase the participants risks. Prior to initiating telemedicine for study visits the

study team will explain to the participant, what a telemedicine visit entails and confirm that the study participant is in agreement and able to proceed with this method. Telemedicine acknowledgement will be obtained in accordance with the Guidance for Use of Telemedicine in Research. In the event telemedicine is not deemed feasible, the study visit will proceed as an in-person visit. Telemedicine visits will be conducted using HIPAA compliant method approved by the Health System and within licensing restrictions.

STUDY CALENDAR: SBRT ARM ONLY

	Pre-Study ^V	Day 1 ^W	Day 61	Day 31 (+/- 7 days)	Day 181 (+/- 7 days)	Day 361 (+/- 7 days)	Follow-up Q6 Month ^T (+/- 7 days)
ICF	X						
Demographics	X						
Medical History	X						
Concomitant Medications	X						
Physical Exam	X						
Performance Status	X						
Vital Signs	X						
Height	X						
Weight	X						
CBC w/ Diff ^A	X ^C						
LDH	X ^C						
Serum Chemistry ^B	X ^C						
Testosterone	X ^C						
PSA	X ^D						
Bone Scan	X ^E						
CT/MRI of Involved Site ^I	X ^E						
PSMA-PET/CT	X ^R						
CAPP-seq ^J							
EPIC HD-CTC ^K							
Immuno-SEQ ^L							
Immunophenotyping ^M							
Invitae ^N							
Rectal Swab ^O							
AE Evaluation ^U							
QoL Brief Pain Inventory							
SBRT/SABR ^P							

Randomization to SBRT arm

A.	CBC w/ Diff includes: White Blood Cell Count, Red Blood Cell Count, Hemoglobin, Hematocrit, Mean Corpuscular Volume, Mean Corpus HgB, Mean Corpus HgB Conc, RBC Distribution Width, Platelet Count, Neutrophils %, Lymphocyte %, Monocyte %, Eosinophil %, Basophil %, Absolute Neutrophil Count, Absolute Lymphocyte Count, Absolute Monocyte Count, Absolute Eosinophil Count, Absolute Basophil Count, Immature Granulocyte %, and Absolute Immature Granulocyte Count.
B.	Serum Chemistry (CMP) includes Sodium, Potassium, Chloride, Carbon Dioxide (bicarbonate), Urea Nitrogen, Serum Creatinine, Est GFR Afr-Am(MDRD Eqn), Est GFR NonAfrAm(MDRD Eqn), Glucose, Calcium, Total Protein, Albumin, Total Bilirubin, Alkaline Phosphatase, Aspartate Amino Trans (AST), Alanine Amino Trans (ALT), Anion Gap, BUN/Creatinine Ratio, and AST/ALT ratio.
C.	CBC w/ Diff, LDH, Serum Chemistry, and Testosterone labs must be obtained within 6 months prior to enrollment.
D.	PSA lab must be obtained within 1 month prior to enrollment.
E.	Pre-study Bone Scan and CT/MRI need to be obtained within 3 months prior to enrollment. PET-CT scan is an alternative for study entry imaging to CT/MRI and/or Bone Scan
F.	Medical history review, concomitant medication review, physical exam, performance status assessment, adverse event evaluation, and the brief pain inventory assessment should be performed once , during either Day 1 or sometime during a SBRT visit (e.g. OTV).
G.	Invitae test should be performed at any time during the study or after follow up for all enrolled patients.
H.	Correlative study blood specimens should be drawn after standard of care labs, from the same line, to prevent epithelial cells from contaminating blood specimens.
I.	CT/MRI or Axumin/Choline/DCFPyL PETs should be used to measure tumor dimensions at baseline and to measure tumor dimensions and evaluate radiographic response on day 181 and on day 361. Imaging used at baseline can be further used at Day 180 and Day 360, respectively.
J.	Instructions for CAPP-Seq Sample Collection & Processing can be found in Appendix III of the protocol.
K.	Instructions for EPIC-HD CTC Sample Collection & Processing can be found in Appendix IV of the protocol.
L.	Instructions for ImmunoSeq Sample Collection & Processing can be found in Appendix V of the protocol.
M.	Instructions for Immunophenotyping Sample Collection & Processing can be found in Appendix VIII of the protocol. Only applicable for JHU/JHSOM. Not applicable for outside sites.
N.	Instructions for Invitae Saliva Kit Sample Collection can be found in Appendix VII of the protocol.
O.	Instructions for Rectal Swab Collection for Microbiome Analysis can be found in Appendix VI of the protocol.
P.	Instructions for SBRT/SABR treatment planning can be found in section 6.3 of the protocol.
Q.	After randomization, only interval concomitant medications, interval medical history, and limited physical exam information needs to be collected. This only needs to occur once, either on Day 1 visit or during SABR treatment.
R.	Per SOC, patient's will have a PSMA PET/CT prior to enrollment/randomization. Patients who are still enrolled in the trial will have a PSMA PET/CT 360 Days from initial PSMA PET/CT (see S).
S.	ONLY for sites participating in PSMA PET-CT: If applicable, patient's will have a PSMA PET/CT 12 Months from the second completed PSMA PET (~approximately 13/14 months from randomization)
T.	Additional follow-up visits are for 1 year. Follow up after 12 months will be conducted Q6 months, as SOC (months 18 and 24).
U.	All AEs will be collected using CTCAE version 4.0. All skeletal related events will need to be collected throughout the trial and during the follow-up period.
V.	If Pre-study and Day 1 occurs within 2 weeks of each other, the following labs do not need to be repeated for Day 1: PSA, LDH, Testosterone, CBC w/Diff, and CMP. If PSA is completed within 2 weeks from Day 1, regardless of Footnote D, then it may be used. If PSA has been drawn greater than 2 weeks from Day 1, then it must be repeated. Research Blood for Day 1 MUST be completed PRIOR to SABR and/or Xofigo (Radium-223) injection.
W.	During 18 and 24 month follow-up: limited physical exam, ECOG (performance status) changes to conmedications, changes to medical history, Adverse Events, BPI (QoL), and PSA are required for documentation (Epic Note). Any additional labs or imaging are at the discretion of the treating physician.

STUDY CALENDAR: SBRT + Xofigo ARM

	Pre-Study ^Y	Day 1 ^Y	Day 15	Day 29	Day 43	Day 57	Day 61	Day 71	Day 85	Day 31 (+/- 7 days)	Day 39	Day 113	Day 127	Day 141	Day 155	Day 181 (+/- 7 days)	Day 361 (+/- 7 days)	Follow-up Q6 Month ^W (+/- 7 days)
ICF	X																	
Demographics	X																	
Medical History	X									X ^T						X ^T	X ^T	X ^Z
Concomitant Medications	X									X ^T						X ^T	X ^T	X ^Z
Physical Exam	X									X ^T						X ^T	X ^T	X ^Z
Performance Status	X									X ^F						X	X	X ^Z
Vital Signs	X									X								
Height	X									X								
Weight	X									X								
CBC w/ Diff ^A	X ^C									X ^I						X	X	X ^Z
LDH	X ^C									X ^I						X	X	X ^Z
Serum Chemistry ^B	X ^C									X ^I						X	X	X ^Z
Testosterone	X ^C									X ^I						X	X	X ^Z
PSA	X ^D									X ^I						X	X	X ^Z
Bone Scan	X ^E									X ^I						X	X	X ^Z
CT/MRI/Axumin or Choline PET of Involved Site ^K	X ^E									X ^I						X	X	X ^Z
PSMA-PET/CT	X ^U									X ^I								
CAPP-seq ^L										X ^H						X ^H	X ^H	
EPIC HD-CTC ^M										X ^H						X ^H		
Immuno-SEQ ^N										X ^H								
Immunophenotyping ^O										X ^H						X ^H	X ^H	
Invitae Test ^P																		
Rectal Swab ^Q																		
AE Evaluation ^X																X	X	X
QoL Brief Pain Inventory																X	X	X
SBRT/SABR ^R																		
Xofigo ^S																		

Randomization to SBRT + Xofigo arm

A.	CBC w/ Diff includes: White Blood Cell Count, Red Blood Cell Count, Hemoglobin, Hematocrit, Mean Corpuscular Volume, Mean Corpus Hgb, Mean Corpus Hgb Conc, RBC Distribution Width, Platelet Count, Neutrophils %, Lymphocyte %, Monocyte %, Eosinophil %, Basophil %, Absolute Neutrophil Count, Absolute Lymphocyte Count, Absolute Monocyte Count, Absolute Eosinophil Count, Absolute Basophil Count, Immature Granulocyte %, and Absolute Immature Granulocyte Count.
B.	Serum Chemistry (CMP) includes: Sodium, Potassium, Chloride, Carbon Dioxide (bicarbonate), Urea Nitrogen, Serum Creatinine, Est GFR Afr-Am(MDRD Eqn), Est GFR NonAfr-Am(MDRD Eqn), Glucose, Calcium, Total Protein, Albumin, Total Bilirubin, Alkaline Phosphatase, Aspartate Amino Trans (AST), Alanine Amino Trans (ALT), Anion Gap, BUN/Creatinine Ratio, and AST/ALT ratio.
C.	CBC w/ Diff, LDH, Serum Chemistry, and Testosterone labs must be obtained within 6 months prior to enrollment.
D.	PSA lab must be obtained within 1 month prior to enrollment.
E.	Pre-study Bone Scan and CT/MRI need to be obtained within 3 months prior to enrollment. PET-CT scan is an alternative for study entry imaging to CT/MRI and/or Bone Scan.
F.	Medical history review, concomitant medication review, physical exam, performance status assessment, adverse event evaluation, and the brief pain inventory assessment should be performed only once , either during Day 1 or during the SBRT visit (e.g. OTV).
G.	Invitae test should be performed at any time during the study or after follow up for all enrolled patients.
H.	Correlative study blood specimens should be drawn after standard of care labs, from the same line, to prevent epithelial cells from contaminating blood specimens.
I.	CBC w/ Diff must be performed and analyzed prior to each Xofigo infusion.
J.	For patients to receive Xofigo infusion #1, the following criteria must be met: 
 • ANC $\geq 1.5 \times 10^3 / \text{L}$ • Platelets $\geq 100 \times 10^3 / \text{L}$ • Hemoglobin $\geq 10 \text{ g / dL}$ For patients to receive Xofigo infusions #2-6, the following criteria must be met: 
 • ANC $\geq 1 \times 10^3 / \text{L}$ • Platelets $\geq 50 \times 10^3 / \text{L}$ If a patient fails to meet the criteria, the criteria should be re-checked every 7-10 days. If the patient does not recover to the required values within 6-8 weeks, further Xofigo treatments should be discontinued.
K.	CT/MRI or Axumin/Choline PETs should be used to measure tumor dimensions at baseline and to measure tumor dimensions and evaluate radiographic response on day 181 and on day 361. Imaging used at baseline can be further used at Day 180 and Day 360, respectively.
L.	Instructions for CAPP-Seq Sample Collection & Processing can be found in Appendix III of the protocol.
M.	Instructions for EPIC-HD CTC Sample Collection & Processing can be found in Appendix IV of the protocol.
N.	Instructions for ImmunoSeq Sample Collection & Processing can be found in Appendix V of the protocol.
O.	Instructions for Immunophenotyping Sample Collection & Processing can be found in Appendix VIII of the protocol. Only applicable to JHU/JHSOM. Outside sites will not be performing Immunophenotyping.
P.	Instructions for Invitae Saliva Kit Sample Collection can be found in Appendix VII of the protocol.
Q.	Instructions for Rectal Swab Collection for Microbiome Analysis can be found in Appendix VI of the protocol.
R.	Instructions for SBRT/SABR treatment planning can be found in section 6.3 of the protocol.
S.	Instructions and information for Xofigo (Radium-223) can be found in section 6.3 of the protocol.
T.	After randomization, only interval concomitant medications, interval medical history, and limited physical exam information needs to be collected only once, either during Day 1 visit or during SABR.
U.	Per SOC, patient's will have a PSMA PET/CT prior to enrollment/randomization. Patients who are still enrolled in the trial will have a PSMA PET/CT 360 Days from initial PSMA PET/CT (see V).
V.	ONLY for sites participating in PSMA PET-CT - If applicable, patient's will have a PSMA PET/CT 12 Months from the first completed PSMA PET ("approximately 13/14 months from randomization")
W.	Additional follow-up visits are for 1 year. Follow up after 12 months will be conducted @6 months, as SOC (months 18 and 24)
X.	All AEs will be collected using CTCAE version 4.0. All skeletal related events will need to be collected throughout the trial and during the follow-up period.
Y.	If Pre-study and Day 1 occurs within 2 weeks of each other, the following labs do not need to be repeated For Day 1: PSA, LDH, Testosterone, CBC w/Diff, and CMP. If PSA is completed within 2 weeks from Day 1, regardless of Footnote D, then it may be used. If PSA has been drawn greater than 2 weeks from Day 1, then it must be repeated. Research Blood for Day 1 MUST be completed PRIOR to SABR and/or Xofigo (Radium-223) injection.
Z.	During 18 and 24 month follow-up: limited physical exam, ECOG (performance status) changes to conmedications, changes to medical history, Adverse Events, BPI (QoL), and PSA are required for documentation (Epic Note). Any additional labs or imaging are at the discretion of the treating physician.

